- c. Undergone expansion treatment in the upper arch causing an arch width increase of 3-10mm, either using a Quadhelix, Rapid Maxillary Expansion, expansion with archwires, or URA with midline screw. Patients' interarch measurements at the time of debond will be compared with their interarch measurements using the pre-treatment model available at the clinic.
- d. No chronic medical conditions

The criteria for suspending or terminating the study are:

- a. Relapse due to compliance issue
- b. Relapse due to investigative product
- c. Subject did not come for follow-up

The subject withdrawal criteria are:

- a. Voluntary

If relapse is found and/or if subjects request to withdraw from the study, subjects will be informed that they will not need to take impressions at follow-up but they still can make appointment with their orthodontist for a normal retainer review. If insignificant relapse is found, new Hawley retainers will be provided free of charge. If significant relapse is found in subjects from intervention group, free treatment will be provided. The withdrawn subjects will not be replaced and an Intention to Treat analysis (ITT) will be done.

The generation of randomization sequence will be performed in blocks of 12 to ensure that equal number of patients was allocated to each of the two retention groups. A randomized generator will be used for allocation. In this multi-centre trial, a centralized randomization technique which incorporated external involvement is used. Individuals who recruit subjects from each centre will contact a central methods centre by phone after patient enrolled in order to prevent selection bias and protect the assignment sequence until allocation. Calibrated researcher will collect the study models which the ID and intervention are covered by opaque tape once they are ready for measurement. Only one dental cast at a time will be picked out of its box without showing any previous measurements. Two dental casts from the same patient will not be measured in connection with each other. Due to the prospective nature of the study, it was inconvenient to anonymize dental casts from the start of the study.

Hawley retainer
(coverage)

Normal VFR retainer

Modified VFR (palatal

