5.2 Study design

This is a prospective randomised controlled trial to evaluate the differences in relapse after expansion treatment between a Hawley and a modified vacuum formed retainer.

The study will involve:

- a. **Clinical:** An upper and lower impression with alginate will be taken for dental cast and retainer construction. **This procedure is a normal procedure done in all orthodontic appointments upon removal of fixed appliances.** However one extra upper impression will be taken for the research. It will take approximately 5-10 minutes. **All retention appliances will be distributed within 24 hours after debonding. The retainers will be washed under tap water before delivering to the patient. When subjects are given the retainers, clinicians will provide post-debond instructions, where the patient has to wear the retainers for 24 hours except during eating and brushing their teeth. Researcher will send reminders of wearing retainer in 1-month interval to ensure they are following the instructions and to enquire if they have any problems.** The patients will be instructed to wear the retainers for 24 hours for the next 6 months and night-time only for month 7 to month 12. At a 3 month and 6 month follow-up, an upper alginate impression will be taken for a dental cast construction at each follow-up visit. **Clinical examination will allow clinician to detect relapse which is by examining the arch width.** The whole duration of participation of each patient may total up to 40 minutes overall. If any unknown allergic reaction to alginate impression occurs, the procedure will be terminated immediately and appropriate first aid action will be given to participant, however these will most likely be anticipated as these subjects have had impressions taken at the start of treatment.
- b. **Data Measurement:** Dental casts will be analysed using digital callipers and arch width will be recorded in the posterior region.
- c. **Data analysis:** Data will be analysed using SPSS. The descriptive statistics on group level at times corresponding to measurements at removal of fixed appliances (T0), 3 months post retention (T1), 6 months post retention(T2) and 12 months post retention(T3) will be calculated for each variable.

RELAPSE DUE TO POOR COMPLIANCE:

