- Poor compliance can be detected by the clinician, such as poor adaptation to speech, appliance looks “clean”, patient unable to seat and remove the appliance, or appliance is lost and not looked after properly.
- Arch width reduced
- Retainer will not fit in mouth

RELAPSE DUE TO INTERVENTION

- Patient able to adapt to retainers well, good adaptation to speech, appliance looks used, patient able to seat and remove retainers easily
- Arch width reduced
- Retainer should still fit in the mouth if patient wears it all the time

Compliance can be confirmed by the use of Thermosensors. Thermo-sensor is not used in this study because it is costly, not entirely accurate and it will not reflect the real-life situation. Most clinical studies do not use Thermosensors to ensure compliance. Using sensors will give out the Hawthorne effect where subjects will tend to perform better since they are aware of the presence of thermos-sensors. This as mentioned earlier does not reflect the real-life scenario.

Monitoring for adverse events

T0: Removal of braces	T1: 3-month review	T2: 6-month review
-Duration: 10-20 minutes -Subjects who have had 3mm of expansion (compared with pre-treatment models) will be selected, subjects given 5-10 minutes to think if they want to participate -Impression will be taken for construction of retainer and study models which will take 5-10 minutes -Adverse reaction i.e. allergic reaction to the impression material will be monitored however this would have been anticipated or recorded in the notes as these patients	-Duration: 5-10 minutes -Subjects will be reviewed and any adverse effect such as relapse will be detected at this point -An upper impression will be taken -Adverse reaction i.e. allergic reaction to the impression material will be monitored however this would have been anticipated or recorded in the notes as these patients would have had impressions taken at the start of orthodontic treatment. -If any allergic reaction occurs, first aid	-Duration: 5-10 minutes -Subjects will be reviewed and any adverse effect such as relapse will be detected at this point -An upper impression will be taken -Adverse reaction i.e. allergic reaction to the impression material will be monitored however this would have been anticipated or recorded in the notes as these patients would have had impressions taken at the start of orthodontic treatment. -If any allergic reaction occurs, first aid

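### Waiving impressions once relapse is found makes later casts go missing because of the outcome, and the plan gives no method for the missing casts

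*Combined protocol and SAP*

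**What the plan says.** **Relapse rule (5.1 Participants Sampling).** If relapse is found, or a patient asks to withdraw, "subjects will be informed that they will not need to take impressions at follow-up"; ordinary retainer reviews remain open to them. Under the lead-in "The criteria for suspending or terminating the study are", the section lists relapse from poor compliance, "Relapse due to investigative product" and missed follow-up. Voluntary withdrawal is the only withdrawal criterion.

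**Remedies.** Section 5.1 says "If insignificant relapse is found, new Hawley retainers will be provided free of charge" and "If significant relapse is found in subjects from intervention group, free treatment will be provided". Section 5.3 Ethics offers a new Hawley or fixed retreatment for significant relapse with the VFR. Neither section gives a limit in mm for either grade of relapse.

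**Breakage (5.3).** A broken investigational retainer is replaced with a Hawley and the patient is counted as a dropout. Section 5.3 does not itself say that impressions stop.

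**Detection (5.2 Study design).** "Clinical examination will allow clinician to detect relapse which is by examining the arch width". The visit table in 5.2 puts detection and a cast at the same 3- and 6-month reviews: "any adverse effect such as relapse will be detected at this point -An upper impression will be taken".

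**Outcome and analysis.** The hypothesis (3.0) concerns relapse of arch expansion, and 5.4.1 measures arch width on casts at debond, 3, 6 and 12 months. Section 5.1 states: "The withdrawn subjects will not be replaced and an Intention to Treat analysis (ITT) will be done". Section 5.4 compares group means by one-way analysis of variance and says nothing about missing casts.

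**The concern.** The variable that triggers the waiver is the variable under study. Patients with large early loss of width are the ones whose later casts are not taken. If one retainer relapses more, that arm loses more of its worst results.

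Intention to treat fixes the arm in which a patient is analysed; it does not supply a cast that was never made. Recruiting 24 to keep 16 per arm replaces numbers but does not remove selection on the outcome. Masked cast reading cannot help either.

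The trigger is also undefined and uneven. There is no limit in mm, a remedy for significant relapse is stated only for the VFR arm, and the examining clinician can see the appliance.

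Breakage is a separate matter: it is loss after a treatment-related event, not loss decided by arch width. Because 5.3 ties it to the investigational product, it probably falls more on the VFR arm.

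At stake is the conclusion the sponsor expects (section 1.0), that the cheaper retainer does as well as the Hawley.

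**Working it through.** **The plan's own figures.** Section 5.4 gives f = 0.42, 2 groups, 3 measurements, correlation 0.5 and total N = 32.
- λ = 32 × 0.42² × 3 / (1 + 2 × 0.5) = 8.4672; critical F(1, 30) = 4.1709; power 0.8039. This matches the printed output.
- The allowance from 16 to 24 per arm covers a loss of 1 − 16/24 = 33%.
- With all 24 per arm, a two-sided t-test for 2.0 mm (SD 2.0) has power 0.924.

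**Illustration.** The documents give no relapse rate, limit or time course, so these are assumptions:
- mean 12-month loss of 2.5 mm (VFR) and 0.5 mm (Hawley), a true difference of 2.0 mm;
- SD 2.0 mm at each visit (5.1) and a 6- to 12-month correlation of 0.5 (5.4);
- 24 per arm, no other attrition and no stops at 3 months;
- no 12-month cast if 6-month loss exceeds the limit, in either arm;
- a share s of the mean loss reached by 6 months.

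Formulas, with m the 12-month mean:
- z = (limit − s·m)/2.0
- share lost = 1 − Φ(z)
- mean of retained casts = m − 0.5 × 2.0 × φ(z)/Φ(z)

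Worked case, limit 4 mm and s = 1:
- VFR: z = 0.75, 22.7% lost, mean falls by 0.389 to 2.111.
- Hawley: z = 1.75, 4.0% lost, mean falls by 0.090 to 0.410.
- Observed difference: 2.111 − 0.410 = 1.70 mm.

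Power is by non-central t with the retained numbers and truncated SDs. The last column carries the 6-month cast forward for stopped patients.

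| s | Limit (mm) | VFR lost | Hawley lost | Available-cast difference (mm) | Power | Carried-forward difference (mm) |
|---|---|---|---|---|---|---|
| 1 | 5 | 11% | 1% | 1.83 | 87% | 2.15 |
| 1 | 4 | 23% | 4% | 1.70 | 79% | 2.22 |
| 1 | 3 | 40% | 11% | 1.56 | 65% | 2.20 |
| 0.75 | 5 | 6% | 1% | 1.90 | 90% | 2.06 |
| 0.75 | 4 | 14% | 4% | 1.81 | 86% | 2.06 |
| 0.75 | 3 | 29% | 9% | 1.71 | 77% | 2.01 |

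**Stops at 3 months as well.** This simulation assumes mean Hawley loss of 0.5, 0.75 and 1.0 mm at 3, 6 and 12 months, and VFR excess of 1.0, 1.5 and 2.0 mm. Limits of 3, 4 and 5 mm give available-cast differences of 1.60, 1.73 and 1.84 mm (power 65%, 80%, 87%), and carried-forward differences of 1.80, 2.00 and 2.05 mm. With correlation 0.8, limits of 3 and 4 mm give available-cast differences of 1.46 and 1.63 mm.

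**Unequal rule.** Take equal true loss of 1 mm, with VFR patients stopped at 3 mm and Hawley patients at 5 mm (s = 1). Available casts make the VFR look 0.23 mm better; carrying forward makes it look 0.19 mm worse. At s = 0.75 the figures are 0.20 and 0.14 mm.

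**A method that uses earlier casts.** A likelihood estimate using the 6-month cast, with stops decided by that cast's value, returned 2.00–2.01 mm in all six cases and 0.00 under the unequal rule. It would not fully correct stops based on information not in the casts.

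**The case against.** A reader might infer that intention to treat has no data at all for relapsed patients. The documents do not support that: debond and earlier casts exist, and the 5.2 table schedules an impression at the detecting visit. The loss concerns later casts.

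A reader might also treat breakage as a second loss decided by the outcome. Breakage is not arch width, and 5.3 does not say impressions stop. None of the figures concern it.

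A third tempting reading is that the plan is biased toward no difference. That holds only if available 12-month casts are compared, the VFR truly relapses more and the rule is equal. One-way analysis of variance implies such a comparison, but the plan does not specify it, and carrying forward can reverse the direction. No document says clinicians stop VFR patients sooner.

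The time point matters too. No primary visit is named, the impression instruction and visit table in 5.2 stop at 6 months, and the sample size uses three measurements; 12 months appears in 1.0, 5.2(c) and 5.4.1. At 6 months, only stops at 3 months would cost casts, and the tabled model has none.

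The effect may be modest. The sponsor expects minimal relapse, and three of the six cases keep power at 86–90%. Rescue is proper patient protection. All this limits size and direction. It does not remove the waiver or supply a missing-cast method.

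**Conclusion.** The concern holds in a limited form. Followed as written, the plan loses post-detection casts because of the outcome, and nothing elsewhere repairs this. Counting breakage as dropout adds a possible loss that is probably uneven between arms.

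On the stated assumptions, comparing available 12-month casts shrinks a true 2.0 mm difference to about 1.6–1.9 mm, with power of about 65–90% against 92%. This is neither a bound nor a best estimate. With equal true relapse and an equal rule there is no bias. What the documents establish is outcome-dependent loss with no defined handling, not a fixed direction of bias. The change should be made, because these casts cannot be recovered after the trial.

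**What to change.** 1. In 5.1, replace the relapse waiver. Take the scheduled 3-, 6- and 12-month upper casts in every randomised patient after relapse, breakage or a retainer change, unless consent is withdrawn. Take a cast before any replacement retainer or retreatment, and analyse all casts in the allocated arm. State that relapse under the termination criteria ends the assigned retainer, not cast collection. Rescue is not delayed.
2. In 5.3, delete the clause that counts a patient with a replaced broken retainer as a dropout.
3. Replace the relapse texts in 5.1 and 5.3 with one rule: the same limit in mm and the same action in both arms, chosen by the investigators. Record the date and reason of each retainer change.
4. In 5.4, use a mixed model with all visits. Add sensitivity analyses that assign extra loss to missing casts, and that include and exclude casts after fixed retreatment. Setting those casts to missing would again drop the worst relapsers, so neither choice should stand alone.

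**Cost.** Relapsed patients keep impressions that were already scheduled (5–10 minute visits). The rest is protocol wording, one record field and a different model. The effect is diluted after a switch to Hawley. In the s = 0.75 case, with all casts kept and switched VFR patients then losing width at the Hawley rate, the difference is 1.97, 1.93 and 1.86 mm at limits of 5, 4 and 3 mm, with power 92%, 91% and 90%. That is a best case, because it ignores fixed retreatment.

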5.0 METHODOLOGY

5.1 Participants Sampling

The sample will be selected from patients attending for orthodontic debond appointments at the Orthodontic Unit of Universiti Kebangsaan Malaysia (UKM), Klinik Pakar Ortodontik Klinik Kesihatan Bandar Botanik and Unit Pakar Ortodontik Klinik Pergigian Sungai Chua patients. The present practice at all 3 locations constructs Hawley and normal VFR retainers for all orthodontic patients. There are technicians and laboratory facilities to construct normal VFR as well as Hawley retainer. The only difference between modified and normal vacuum formed retainer is the outline of the retainers where the technician would trim the retainer, where it would cover the hard palate. Therefore it is only the location of trimming that is different using the same special trimming appliances for normal VFRs. Clinicians from KKM involved would be [name] [name] and [name] [name]. A screening will be done to select patients who are suitable of the study. Only patients who fulfil the criteria will be invited to participate in this study. Participant will be approached in the dental chair once deemed suitable, and will be given 5-10 minutes to decide on participation of the study. Consent will be gathered from the patients or the carer if the patient is below 18 years of age. The patients will then be randomly allocated into two groups using a randomized number computer generator, either the Hawley or the modified vacuumed formed retainers. The expected sample size to be of statistical significance will be calculated using the formula of sample size calculation relevant to this study. The sample size

calculation is based on a significance level of 0.05 and 80 percent power to detect a clinically meaningful difference of 2.0mm (SD=2.0mm) between the two groups in terms of arch width differences, where this difference are based on previous studies by Tynelius et al. (9) and Shawesh et al. (15). The power analysis gave a total sample size of 16 patients in each group. To account for attrition, 24 patients will be recruited in each group

The inclusion criteria of the subjects that will be included in the study are:

- a. Patients who are at least 13 years old at time of debond.
- b. Treatment plan of extraction or non-extraction followed by straight wire appliances in the upper arch only or both arches

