
would have had impressions taken at the start of orthodontic treatment
 
-Using the randomized generator, patient will be allocated to either a:
 
1- Hawley retainer
 
2-Modified vacuum formed retainer
 
-If any allergic reaction occurs, first aid management will be provided and an alternative impression material will be used
	
management will be provided and an alternative impression material will be used
	
management will be provided and an alternative impression material will be used

--	--	--

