5.4.2 Resources

A researcher will assist in screening and randomizing, while site investigators from MOH and their qualified staff will assist in screening and taking impressions. Technicians will facilitate in preparing the dental casts and retainers. Cast preparation will be done in the dental laboratory of the Faculty of Dentistry, UKM, and dental laboratory of Klinik Pakar Ortodontik Klinik Kesihatan Bandar Botanik and Unit Pakar Ortodontik Klinik Pergigian Sungai Chua.

Equipment that is readily available includes alginate impression material, impression trays, digital callipers, examination tray and data analyses software (SPSS version 17.0)

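### The allocation roles in 5.1, 5.2 and 5.4.2 are not reconciled, and centre appears in neither the allocation nor the analysis; the centre risk is a modest chance imbalance

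*Combined protocol and SAP*

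**What the plan says.** **Allocation procedure.** Section 5.1 says that "a centralized randomization technique which incorporated external involvement is used" and that "Individuals who recruit subjects from each centre will contact a central methods centre by phone after patient enrolled". It gives the purpose as preventing selection bias and protecting the sequence until assignment.

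**Roles.** Section 5.4.2 says: "A researcher will assist in screening and randomizing, while site investigators from MOH and their qualified staff will assist in screening".

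**Visit table.** The T0 column of the table in 5.2 lists selection, impressions and then allocation: "Using the randomized generator, patient will be allocated to either a" Hawley or modified vacuum-formed retainer. It mentions no call and does not say who operates the generator.

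**Sequence.** Section 5.1: "The generation of randomization sequence will be performed in blocks of 12 to ensure that equal number of patients was allocated". One block length is given. Neither varying block lengths nor stratification by centre is mentioned anywhere.

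**Centres.** Three sites recruit, and 5.1 notes that "The present practice at all 3 locations constructs Hawley and normal VFR retainers for all orthodontic patients". Section 5.4.2 names a laboratory for each: "Cast preparation will be done in the dental laboratory of the Faculty of Dentistry, UKM", with those of the two clinics named after it.

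**Analysis.** Section 5.4 compares group means by one-way analysis of variance, with no centre term.

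**The concern.** Two matters are involved, and they should be kept apart.

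The first is who holds the sequence. Eligibility depends on a cast measurement (an increase of 3–10 mm), and the invitation is made at the chairside. Both are open to influence from someone who can foresee the next assignment. The two appliances are visibly different, so those who fit them know past assignments. The safeguard is the central service in 5.1. A site working only from the visit table or the resources paragraph would not learn that it must be used.

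The second is centre. Technicians in three laboratories make the retainers, and clinicians at three sites review the patients. If outcomes differ between sites and one site's patients fall unevenly between the arms, part of that difference enters the treatment comparison. Neither the stated allocation nor the stated analysis removes it.

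**Working it through.** **1. The three descriptions side by side**

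| Place | Who acts | Mechanism |
|---|---|---|
| 5.1 | Recruiter phones a central methods centre after enrolment | Generator, blocks of 12, central, outside involvement |
| 5.4.2 | A researcher assists in screening and in randomising | Not stated |
| 5.2, T0 column | Not stated | Generator; no call mentioned |

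Nothing in the second or third row excludes the first. Equally, no section says who alone holds the sequence, or that screening staff are kept from it.

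**2. The plan's own figure**

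The documents give no figure for predictability or centre balance. The printed power run in 5.4 reproduces:
- λ = N·f²·m / (1 + (m−1)ρ) = 32 × 0.42² × 3 / (1 + 2 × 0.5) = 8.4672.
- The critical F(1, 30) is 4.1709 and the power is 0.8039, as printed.

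**3. Predictability of blocks of 12**

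- With b patients per arm in a block, the expected number of final assignments that are certain to someone who knows all earlier ones is 2b/(b+1). For b = 6 this is 12/7 = 1.71 of 12, or 14%. Simulation gives 1.72, and a best guess that is right 64% of the time against 50% by chance.
- That observer must see every assignment at all three sites, in order, and know where blocks begin.
- A recruiter who sees only one centre's share of a common list (16 of 48 assumed), even if told the block boundaries, has under 0.01% of assignments determined (about 0.007% by simulation).
- For comparison, blocks of 4 seen in full give 2b/(b+1) = 4/3 of 4, or 33% certain.

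**4. Centre imbalance**

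Inputs: 48 patients (24 per arm, 5.1), which is four blocks of 12, and one common list, since no stratification is stated. Centre sizes are not given, so three assumed sets are shown. The simulation used 50,000 runs or more per row.

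| Assumed centre sizes | Some centre differs by ≥4 between arms | by ≥6 (11:5 or worse if 16) |
|---|---|---|
| 16/16/16 | 62% | 27% |
| 24/12/12 | 59% | 24% |
| 30/10/8 | 55% | 19% |

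With 16 per centre, 12:4 or worse in some centre has a chance of 8%. If the list were stratified by centre in blocks of 4 (illustrative), a difference of 4 or more could not occur.

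**5. What the imbalance does to the result**

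- Suppose one centre's patients differ by δ mm. The arm difference then shifts by δ(a − b)/24, where a and b are that centre's numbers in the two arms.
- With 16 per centre, the mean of |a − b| is 2.56. For an assumed δ = 1 mm the average absolute shift is 2.56/24 = 0.11 mm. For δ = 0.5 mm it is 0.05 mm, and for δ = 2 mm it is 0.21 mm.
- An 11:5 split gives 6/24 = 0.25 mm at δ = 1 mm. A given centre differs by 6 or more in about 12% of trials.
- For scale, the target difference is 2.0 mm, and the standard error with SD 2.0 mm and 24 per arm is 2.0 × √(2/24) = 0.58 mm.

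**6. Cost of a centre term**

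Three centres use two degrees of freedom. In the plan's own power run, going from 30 to 28 error degrees of freedom at the same λ moves the critical F from 4.171 to 4.196 and the power from 0.804 to 0.802.

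**The case against.** Section 5.1 sets out one explicit procedure with external, central concealment, and it mentions the generator just before it describes that service. The visit table may simply be naming the same system. That table is headed as monitoring for adverse events and is not a procedure for allocation. In 5.4.2 the researcher only assists, and placing the telephone call would count as assisting. On this reading nothing conflicts. This largely stands, and it limits the first part of the point to a clarification of roles.

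A reader might infer that a screening researcher performs the allocation, so that selection bias is likely and 14% of assignments can be foreseen. The documents do not support this. They do not say that the researcher holds or runs the sequence, and nobody is described as seeing every assignment at all three sites. A recruiter at one site can determine almost nothing from a common list, and blocks of 12 are harder to predict than short ones.

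On centre, it can be said that all three sites already make both standard appliances, that the modified retainer differs only in where it is trimmed, that no evidence of a centre effect is cited, and that the expected shift is small beside the 2.0 mm target. All of this is fair. It makes the centre term an inexpensive improvement and does not make its absence an error. It does not remove the chance imbalance, which the stated analysis leaves in place.

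**Conclusion.** The point holds in two limited parts.

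First, the sections leave it unsettled who holds and runs the sequence. They can be reconciled in favour of 5.1, in which case selection bias is largely prevented. A breach of concealment is not shown.

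Second, centre is absent from the stated allocation and analysis. With one common list and 16 patients per centre, there is about a 27% chance of an 11:5 or worse split in some centre; under the other assumed sizes, the chance of a difference of 6 or more is 19–24%. A reader might take this as a bias toward one retainer. It is not: the imbalance is random and favours neither arm in expectation. With an assumed 1 mm effect in one of three equal centres, the shift averages about 0.11 mm and reaches 0.25 mm or more in about 12% of trials. The centre sizes, the centre effect and the single list are assumptions; the documents give no figure for the first two and do not state the third outright. The planned sample size is not affected.

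**What to change.** 1. Make the telephone procedure in 5.1 the only allocation procedure. State that the central methods centre alone holds and runs the sequence.
2. Amend the T0 column in 5.2 and the roles in 5.4.2 to match: staff who screen or measure do no more than phone the central centre, once consent and eligibility are on record.
3. Include centre as a factor in the primary between-group model in 5.4.
4. If the central list is also stratified by centre, use randomly varied block sizes that are not disclosed to sites. Small fixed blocks within a centre would be easier to predict than the present list, because each site would then see its own sequence in full.

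**Cost.** Items 1 and 2 are wording. Item 3 uses two degrees of freedom, about 0.2 percentage points of power in the plan's own calculation. Item 4 needs a new central list and may leave the arm totals slightly unequal. The sample size does not change.
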